- i. Patient in stable condition, as determined by attending physician
- ii. Patient has an EAF in the setting of OA
- iii. Patient EAF is determined to require surgical resolution

b. Exclusion Criteria:

- i. Patient unstable, as determined by attending physician
- ii. Patient deemed to be at significant risk of complication

Attachments

Subject Recruitment Methods & Privacy: Using active voice, describe plans for the identification and recruitment of subjects, including how the population will be identified, and how initial contact will be made with potential subjects by those having legitimate access to the subjects' identity and the subjects' information.

Describe the setting in which an individual will be interacting with an investigator or how and where members of the research team will meet potential participants. If applicable, describe proposed outreach programs for recruiting women, minorities, or disparate populations as participants in clinical research. Describe steps taken to minimize undue influence in recruiting potential participants.

Please note: Based upon both legal and ethical concerns, the UK IRB does not approve finder's fees or "cold call" procedures made by research staff unknown to the potential participant. The ORI/IRB does not control permission to any UK listserv, mass mailing list, etc. Investigators must secure prior approval for access and use from owners/managers.

For additional details, see topic "Recruitment of Subjects/Advertising" on ORI's [IRB Survival Handbook web page](#) and the PI Guide to Identification and Recruitment of Human Subjects for Research [\[PDF\]](#).

Patients will be identified by the principal investigator or via CCTS data push review. CCTS analysts will configure a data 'push' within the electronic medical record that will send a daily list of patients meeting some of the study criteria to approved study personnel. This list will include hospital medical record numbers, which will be used to further review patients for eligibility. When a patient is deemed eligible, approved study personnel will approach the patient/LAR for informed consent. If consent is obtained, the research procedures will begin immediately, and data collection initiated. Patients that refuse study participation will receive standard care as determined by their attending physician.

[Back to Top](#)

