Research Procedures: Describe the research procedures that will be followed. Identify all procedures that will be carried out with each group of subjects. Differentiate between procedures that involve standard/routine clinical care and those that will be performed specifically for this research project.

Study participants will receive a custom manufactured device to isolate effluent from their EAF. Prior to device production, research personnel will draft a digital rendering from either a recent abdominal CT scan or physical measurements of the patient's fistula and wound bed. The Computer Aided Design (CAD) program used to draft and render the device will be AutoDesk Fusion360. Once the digital draft is prepared, a negative mold will be generated. The negative mold is then exported as a buildable file to a 3D printer. 3D printing facilities used in this study will be in-house through the UK General Surgery CATS (Center for Advanced Technology and Stimulation). Printers used will be a Makerbot 2X FDM printer. Using this printer, a mold of the custom device will be manufactured, and then by pouring liquid resin into the mold, and allowing it to cure (solidify), the device will be produced.

Silicone has historically been used in many various medical applications. Its safety and its biocompatibility has been documented for applications far more rigorous than the one being described here. Following production, the complete silicone device will immediately be available for cleansing, and transport to the acute care ward by research personnel. The device will be applied to the patient by his/her nursing staff at the next dressing change. The device is designed to smoothly fit over the patient's fistula and seal to the base of the wound. It will provide enough support to anchor surrounding dressings, resist collapse, and be malleable enough to not cause significant discomfort to the patient. The underlying and surrounding wound bed will be dressed as normal at the nursing staff's discretion. An ostomy bag may be attached to the anterior phalange of the device with stoma paste, and its contents emptied as necessary. An abdominal binder will hold the device in place, flush with the surrounding skin.

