If the research includes survey or interview procedures, the questionnaire, interview questions or assessment scales should be included in the application (use attachment button below).

The data collection instrument(s) can be submitted with your application in draft form with the understanding that the final copy will be submitted to the IRB for approval prior to use (submit final version to the IRB for review as a modification request if initial IRB approval was issued while the data collection instrument was in draft form).

Note: The IRB approval process does not include a statistical review. Investigators are strongly encouraged to develop data management and analysis plans in consult with a statistician.

Data collection will be conducted by study personnel or participating healthcare staff and stored in a secure online application (Sharepoint) within the University of Kentucky.

Primary data points to be collected:

- a. Patient satisfaction/quality of life, as determined by pain rating, mobility scale, and subjective satisfaction questionnaires
 - i. Pain rating 1-10
 - ii. Mobility scale-standard assessment at UK (similar to BMAT)
 - iii. Patient satisfaction can be a version of TAM (technology acceptance model) model, tweaked for patients instead of providers. Give at study completion. Focus on intention to use in future and ease of use.
- b. Number of required dressing changes per day (fistula-specific dressing changes)
- c. Average time of required fistula-specific dressing changes
- d. Terminal wound management that the patient is transitioned to upon study completion
- e. Listing of supplies used each fistula-specific dressing change
- f. Assessment of new technology acceptance by staff-TAM model. Give TAM to nursing staff at study's completion.
- g. If possible and if patient consent is obtained, we will video record the first few device applications/dressing changes per patient case. We will use this video evidence to better design application protocols and strategies in the future.

h. Adverse event assessment form-see Attachment B.

Secondary data points to be analyzed (following study completion):

i. Cost of patient management with device (estimate per week)

j. Effectiveness of device isolation, as determined by infection/complication occurrence, observed leakage, hospital LOS, and resolution times.

Attachments

Attach Type	File Name
DataCollection	Inpatient Data Collection Form rev1 clean.pdf

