Costs to Subjects: Describe any costs for care associated with research (including a breakdown of standard of care procedures versus research procedures), costs of test drugs or devices, and research procedure costs that are the subject's responsibility as a consequence of participating in the research. Describe any offer for reimbursement of costs by the sponsor for research related injury care.

None

Data and Safety Monitoring: The IRB requires review and approval of data and safety monitoring plans for greater than minimal risk research, clinical research, or NIH-funded/FDA-regulated clinical investigations.

If you are conducting greater than minimal risk research, clinical research, or your clinical investigation is NIH-funded/FDA-regulated, describe your Data and Safety Monitoring Plan (DSMP). [Click here for additional guidance on developing a Data and Safety Monitoring Plan.](#)

If this is a *non-sponsored investigator-initiated* protocol considered greater than minimal risk research, clinical research, or your clinical investigation is FDA-regulated, and if you are planning on using a Data and Safety Monitoring Board (DSMB) as part of your DSMP, [click here for additional guidance](#) for information to include with your IRB application.

If relying on an independent agent or committee for DSMB services, it is the PI's responsibility to establish the services with the agent or committee. Please be reminded that the PI must submit DSMB reports to the IRB via modification or continuing review. 

A Data and Safety Monitoring Board will be created to objectively evaluate the study results throughout the course of the study. This board will examine patient adverse events and patient outcomes. The Data and Safety Monitoring Board will consist of a physician (surgeon) and a nurse not affiliated with the study in any way. The DSMB will meet twice for each patient; at 2 weeks post-device initiation or prior to discharge (whichever is first), and at 2 months post-device initiation. The DSMB will review real time data collected by the investigators regarding device usage as detailed in the Data Collection sub-section.

Our Data and Safety Monitoring Plan will include criteria for stopping study enrollment and terminating device usage. These include:

- i. Development of an acute allergic reaction following device usage
- ii. Development of a new EAF, from device use or originating spontaneously

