- iii. Inability to manage device usage at home, as determined by the investigative team
- iv. Unsatisfactory effluent control, as determined by the investigative team

1. Persistent inability of the device to control fistula contents, even after remodeling, refitting, and other modifications have been attempted.

Adverse Events and Serious Adverse Events will be reported per IRB guidelines. Our AE assessment guide is attached (attachment

B). Complications associated with clinical care and underlying disease, and not related the EAF (section 1.1), will not be reported. Patient safety will be monitored normally by hospital staff.

[Back to Top](#)

Subject Complaints: Describe procedures (other than information provided in consent document) for handling subject complaints or requests for information about the research. The procedures should offer a safe, confidential, and reliable channel for current, prospective, or past research subjects (or their designated representative) permitting them to discuss problems, concerns and questions, or obtain information.

If any patient has a complaint at any time during study participation, they may contact their healthcare team or the research personnel and their issues will be discussed. All patients have the right to discontinue study participation at any time.

Does your research involve **Non-English Speaking Subjects or Subjects from a Foreign Culture?**

Yes No

—Non-English Speaking Subjects or Subjects from a Foreign Culture—

Describe how information about the study will be communicated to potential subjects appropriate for their culture, and if necessary, how new information about the research may be relayed to subjects during the study.

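### The listed stopping criteria do not name death, serious infection or serious skin/wound breakdown at the device site, and no event-triggered DSMB review is described

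*Protocol*

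**What the plan says.** **Criteria.** Research Description, Data and Safety Monitoring: "Our Data and Safety Monitoring Plan will include criteria for stopping study enrollment and terminating device usage". Four follow, introduced as an open list:

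- (i) an acute allergic reaction;
- (ii) a new enteroatmospheric fistula (EAF), whatever its origin;
- (iii) inability to manage the device at home;
- (iv) effluent control that the investigative team finds unsatisfactory. A sub-item describes this as persistent failure after remodeling and refitting have been tried.

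**DSMB.** An unaffiliated surgeon and nurse examine adverse events and outcomes through the study. They review real-time data of the kinds listed under Data Collection, where item h is the adverse event form. The board is to "meet twice for each patient; at 2 weeks post-device initiation or prior to discharge (whichever is first), and at 2 months post-device initiation". No other meeting is described.

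**Reporting.** "Adverse Events and Serious Adverse Events will be reported per IRB guidelines". One exclusion follows: "Complications associated with clinical care and underlying disease, and not related the EAF (section 1.1), will not be reported".

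**Reversion.** Under Resources, patients return at once to standard wound care if the device is deemed unsafe or riskier than standard management. The clause mentions neither the DSMB nor enrollment.

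**Infection as an outcome.** Data Collection item j is "Effectiveness of device isolation, as determined by infection/complication occurrence, observed leakage, hospital LOS, and resolution times". It stands under the heading "Secondary data points to be analyzed (following study completion").

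**Fitting.** Subject Recruitment: "If consent is obtained, the research procedures will begin immediately, and data collection initiated". Research Procedures describes design, mold printing, casting and curing, then: "The device will be applied to the patient by his/her nursing staff at the next dressing change".

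**The concern.** The protocol itself makes the unnamed events foreseeable. The Background reports high mortality in this condition, says that leaked effluent leads to inflammation and infection, and says that it can damage skin. Data Collection item j treats infection and complications as evidence on whether the device isolates effluent. A serious wound infection could therefore be the clearest sign that the device has failed, yet it is not a listed criterion, while a practical difficulty with home care is.

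At stake is who looks at such an event before the device goes onto another patient. The study has five patients, no control group and a device made in-house, so a single event carries much of the safety information. The independent board exists to judge that information, but the plan gives no step that brings it a death or a serious device-site infection before the next fitting.

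**Working it through.** The protocol states no event rate, boundary or alert deadline, so there is no figure to reproduce. The check sets the text against the events and then works through the calendar.

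**1. Criteria against events**

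| Criterion | Death | Serious infection | Serious skin/wound breakdown |
|---|---|---|---|
| i. Acute allergic reaction | not named | not named | not named |
| ii. New EAF | not named | not named | not named |
| iii. Home management | not named | not named | not named |
| iv. Effluent control | not named | indirectly, if leakage is the cause | indirectly, if leakage is the cause |

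None of the 4 names these events. Criterion iv can reach infection or skin damage through leakage, and it belongs to a list that stops enrollment. But it rests on the team's judgment of effluent control, described as persistent failure after refitting. One septic or fatal event need not meet it.

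**2. Interval between a patient's two meetings**

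Inputs (DSMB schedule): first meeting by day 14, second at 2 months, taken as 61 days.

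- 61 − 14 = 47 days; with 2 months as 59 to 62 days, 45 to 48.
- If discharge brings the first meeting to day 7: 61 − 7 = 54 days. To day 3: 61 − 3 = 58 days.

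In all there are at most 5 × 2 = 10 scheduled meetings. Another patient's meeting may fall inside the interval, but only by chance.

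**3. Device use after the last scheduled meeting**

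For L months of use, the share is max(0, L − 2)/L. The protocol does not fix L. Outpatient monitoring runs to fistula resolution or study termination (Research Procedures), and the Background gives 6 to 12 months on average from fistula development to surgery.

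| Assumed L (months) | Share after last meeting |
|---|---|
| 2 or less | 0% |
| 4 | 2/4 = 50% |
| 6 | 4/6 = 67% |
| 12 | 10/12 = 83% |

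The 83% assumes that the device starts when the fistula develops and is used for 12 months. A late start, discharge without home use, or a change of wound care shortens L. Only the range 0% to 83% is supported.

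**4. Next patient**

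Between consent and fitting lie design, mold printing, casting, curing and cleaning. Their duration is not given, and no stated rule uses that time for a safety review.

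**5. How often a trigger might be used**

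The protocol gives no rate. With an assumed per-patient risk p, the chance of at least one event in 5 patients is 1 − (1 − p)^5: 0.23 at 5%, 0.41 at 10%, 0.67 at 20%, 0.83 at 30% and 0.92 at 40%. This is illustration only.

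**The case against.** The case for the plan is substantial. The DSMB is independent and sees adverse event data in real time. Serious adverse events go to the IRB. Patients can be taken off the device at once, and if it were judged unsafe the team would hardly fit another. The list is open. Attachment B, the IRB guidelines and the abbreviated IDE requirements that the investigator accepts are not shown and may require prompt escalation. For five patients, named triggers could be called a matter of preference.

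Most of this stands, and it rules out several stronger readings that a reader might infer:

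- *Nothing in the plan can stop enrollment after harm.* Not so: the list, including criterion iv, is expressly for stopping enrollment.
- *Infections are looked at only after the study ends.* Not so: that timing governs secondary items i and j. The adverse event form is item h, and the DSMB reviews it during the study.
- *A new patient is fitted straight after consent.* Not so: manufacture comes between.
- *Device-site infection escapes reporting.* The exclusion covers only complications unrelated to the EAF. Infection or breakdown at the fistula site is on its face related. Some deaths might be excluded, and the text does not say who decides.
- *A patient's first DSMB meeting falling after the fitting is a flaw.* Any schedule counted from device start has that feature.

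What remains is that reviewing real-time data describes what the board sees, not when it is alerted or must meet. The reversion clause names no event and no decision-maker.

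**Conclusion.** The point holds as a cheap improvement to the monitoring plan, not as a misstatement in it. None of the four listed criteria names death, serious wound or systemic infection, or serious skin or wound breakdown at the device site. The only described DSMB meetings are two per patient, about 47 days apart and ending at 2 months. Followed as written, a new patient could be fitted after a device user's death or serious device-site infection without DSMB review.

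Such an event would not go unsupervised, since the clinical team can revert patients and the IRB receives reports. The time without a scheduled meeting for a given patient cannot be reduced to one figure, because length of device use is not fixed. The conclusion rests on the text shown. If Attachment B or the IRB guidelines already require prompt DSMB notice and a hold on fitting, the gap is closed and the protocol need only say so.

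**What to change.** Add to Data and Safety Monitoring:

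- Any death during device use, or any serious wound or systemic infection or serious skin/wound breakdown at the device site, is sent promptly to the existing DSMB. This applies whatever cause the team assigns, and also after month 2.
- No new patient is fitted until the DSMB records that enrollment may continue.
- If the DSMB finds the event clearly unrelated to the device, it releases the hold quickly, for example by phone or email within 2 working days.

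This is a review trigger, not an automatic stop. Reporting whatever the cause fits the plan's own approach, since criterion ii already counts a new fistula of any origin.

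The cost is a short amendment, with the same two-member board and adverse event data already collected. The downside is occasional unscheduled reviews and short pauses in enrollment, some for background events in a condition with high mortality. The quick release limits these.
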